### **3.1.2 Disease Worsening**

After randomization, disease worsening for the study is defined as:

- SDAI > 3.3 and ≤ 11 on two consecutive visits at least two weeks apart OR
- SDAI > 3.3 and ≤ 11 on three or more separate visits OR
- SDAI > 11 at anytime

Disease worsening may be assessed at a regularly scheduled visit or at a Disease Assessment visit as described in [Section 7.2.7](#). If subject meets the criteria for disease worsening then new investigational product will be re-dispensed in a blinded fashion. Subjects will remain on study and complete all study visits as per the Schedule of Assessments ([Table 1](#)).

The overall study design is described by a [study schema](#) at the end of the protocol synopsis section. The study endpoints are defined in [Section 10.1.1](#).

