Disease-Worsening Date (DW Date)

A subject's Disease-Worsening Date is the first Visit Date in which the subject meets the definition for Disease-Worsening. With the exception of analysis using multiple imputation method, Disease-Worsening classification is based on observed SDAI values only. Each subject will have at most one DW Date. A subject's disease-worsening date is used to define his/her Disease-Worsening Baseline.

Rescue Date

A subject's rescue date is the Visit Date in which he or she first receives rescue therapy as identified by the Investigational Product Administration (Rescue Therapy Etanercept) or Investigational Product Administration (Rescue Therapy Methotrexate) form.

Rescue Therapy Period

For the Rescue Analysis Set as defined in [Section 7.4](#), the Rescue Therapy Period begins with the Rescue Date through the EOS Date.

Disease-Worsening Analysis Visit (DW_visit)

The DW_visit defines the analysis visit after a subject fulfills disease-worsening criteria. Details of DW_visit derivation are in [Appendix A](#).

Rescue Analysis Visit (Rescue_visit)

Rescue_visits define the analysis visits after a subject initiates rescue therapy. Details of Rescue_Visit derivation are in [Appendix A](#).

End of Treatment (EOT)

The End of Treatment for a subject is the subject's last assessment for the protocol-specified treatment phase of the study.

End of Study Date

The End of Study Date for a subject is the date the subject completes the safety follow-up phone call, or the date of the Early Termination (ET) visit if no safety follow-up phone call is completed. The date the subject has ended the study is recorded on the End of Study Electronic Case Report Form (eCRF).

End of Study

The End of Study is the date when the last subject across all sites is assessed or receives an intervention for evaluation in the study (ie, last subject last visit).

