6.4 Derived Variables

Duration of Rheumatoid Arthritis

The number of years between the date of diagnosis (DXDT) and Run-in Day 1, rounded to one decimal place, is given by formula below to calculate the duration:

Observed portion	Missing portion	Formula to Calculate Duration
Year, Month, Day		$(\text{Run-in Day 1} - \text{DXDT} + 1)/365.25$
Year, Month	Day	$[\text{Year}(\text{Run-in Day 1}) - \text{Year}(\text{DXDT})] + [\text{Month}(\text{Run-in Day 1}) - \text{Month}(\text{DXDT})]/12$ *if duration equals 0, add 1 month or 1/12 years (to avoid a disease duration of 0)
Year	Month, Day	$[\text{Year}(\text{Run-in Day 1}) - \text{Year}(\text{DXDT})]$ *if duration equals 0, add 1 month or 1/12 years (to avoid a disease duration of 0)

Time to Disease-Worsening

Time to Disease-Worsening = DW Date – Study Day 1 + 1

The subjects without Disease-Worsening will be censored at their last SDAI assessment date.

Only time to subject's *first* instance of disease-worsening will be evaluated.

Time-to-Event (for Rescue Analysis Set)

Time-to-Event = Earliest Date of Achievement of Event of Interest During the Rescue Therapy Period – Rescue Date + 1

For example, for subjects who recapture SDAI remission:

Time-to-Recapture SDAI remission = Earliest Date of Achievement of Observed SDAI remission During the Rescue Therapy Period – Rescue Date + 1

The subjects who do not experience the event of interest will be censored at their last SDAI assessment date.

Only time to subject's *first* instance of each event of interest will be evaluated.

Time-to-Event (for Disease-Worsening Analysis Set)

Time-to-Event = Earliest Date of Achievement of Event of Interest After
Disease-Worsening – DW Date + 1

For example, for subjects who recapture SDAI remission:

Time-to-Recapture SDAI remission = Earliest Date of Achievement of Observed SDAI
remission After Disease-Worsening – DW Date + 1

The subjects who do not experience the event of interest will be censored at their last SDAI assessment date.

Only time to subject's *first* instance of each event of interest will be evaluated.

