- DAS28ESR_remission (< 2.6) = 1, if DAS28-ESR < 2.6;
- DAS28ESR_remission (< 2.6) = missing, if subject has no DAS28-ESR value;
- DAS28ESR_remission (<2.6) = 0, otherwise.

DAS28-ESR LDA

Subjects are classified as achieving DAS28-ESR LDA at a specific timepoint if their DAS28-ESR \geq 2.6 and < 3.2 at that timepoint. Specifically, let DAS28ESR_LDA be defined as follows:

- DAS28ESR_LDA = 1, if DAS28-ESR \geq 2.6 and < 3.2;
- DAS28ESR_LDA = missing, if subject has no DAS28-ESR value;
- DAS28ESR_LDA = 0, otherwise.

DAS28-CRP remission

Subjects are classified as achieving DAS28-CRP remission at a specific timepoint if their DAS28-CRP < 2.6 at that timepoint. Specifically, let DAS28CRP_remission be defined as follows:

- DAS28CRP_remission (< 2.6) = 1, if DAS28-CRP < 2.6;
- DAS28CRP_remission (< 2.6) = missing, if subject has no DAS28-CRP value;
- DAS28CRP_remission (<2.6) = 0, otherwise.

DAS28-CRP LDA

Subjects are classified as achieving DAS28-CRP LDA at a specific timepoint if their DAS28-CRP ≥ 2.6 and < 3.2 at that timepoint. Specifically, let DAS28CRP_LDA be defined as follows:

- DAS28CRP_LDA = 1,
if DAS28-CRP ≥ 2.6 and < 3.2 ;
- DAS28CRP_LDA = missing,
if subject has no DAS28-CRP value;
- DAS28CRP_LDA = 0,
otherwise.

Clinical Disease Activity Index (CDAI)

A composite score that is based on the number of tender and swollen joints using a 28-joint count, PhGA (0-10 visual analog scale), and PtGA (0-10 visual analog scale). A higher score represents worse disease.

Details of the scoring algorithm are described in [Appendix A](#).

Boolean remission status (28-joint count)

A subject achieves Boolean remission (28-joint count) if all of the following criteria are met:

- 28-joint tender joint count ≤ 1 ,
- 28-joint swollen joint count ≤ 1 ,
- CRP (mg/dL) ≤ 1 , and
- patient global assessment ≤ 1 (on a 0-10 scale).

Specifically, let Boolean_28 be defined as follows:

- Boolean_28 = 1,
if a subject fulfills the definition of Boolean remission (28-joint count);
- Boolean_28 = missing,
if any components of the Boolean remission definition are missing;
- Boolean_28 = 0,
otherwise.

Boolean remission (28 joints plus feet/ankles)

A subject achieves Boolean remission (28-joint count plus feet/ankles) if all of the following criteria are met:

- 28-joint plus feet and ankles tender joint count ≤ 1 ,
- 28-joint plus feet and ankles swollen joint count ≤ 1 ,

- CRP (mg/dL) \leq 1, and
- patient global assessment \leq 1 (on a 0-10 scale).

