10.3.3 Missing Components of Composite Endpoints

Missing components of composite endpoints will not be imputed.

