SDAI remission (≤ 3.3) at week 48	
Count (percentage) of subjects achieving SDAI remission as defined by SDAI_remission_maintenance detailed in Section 6.2 at Week 48 for the PAS.
 
A chi-squared test comparing etanercept plus methotrexate combination arm and methotrexate monotherapy using the PAS.
 
Subjects who have a missing SDAI_remission value will be considered as non-responders. Nominal p-values will be provided.
	
Observed_SDAI_remission using as observed approach as detailed in Section 6.5 (missing data will be excluded).
 
Multiple imputation method: impute SDAI values when missing and after rescue for randomized subjects. The composite SDAI values will be imputed rather than its components.

SDAI score and change from baseline at all measured timepoints	
Summary statistics for SDAI score and change from baseline at each Analysis Visit for the PAS.
 
T-test comparing etanercept monotherapy vs methotrexate monotherapy
 
T-test comparing etanercept and methotrexate combination therapy vs methotrexate monotherapy
	
DAS28-ESR and change from baseline at all measured timepoints	
Similar analysis as for SDAI score and change from baseline at all measured timepoints
	

Table 1. Primary and Secondary Endpoints Summary Table

Endpoint	Primary Analysis Method	Sensitivity/Exploratory Analysis
Secondary Endpoints (Continued)		
DAS28-CRP and change from baseline at all measured timepoints	Similar analysis as for SDAI score and change from baseline at all measured timepoints	
CDAI and change from baseline at all measured timepoints	Similar analysis as for SDAI score and change from baseline at all measured timepoints	
SDAI remission (≤ 3.3) at all measured timepoints	Count (percentage) of subjects achieving SDAI remission as defined by SDAI_remission_maintenance detailed in Section 6.5 for the PAS. Chi-squared test comparing etanercept monotherapy vs methotrexate monotherapy Chi-squared test comparing etanercept and methotrexate combination therapy vs methotrexate monotherapy	
Boolean remission at all measured timepoints	Observed count (percentage) of subjects achieving Boolean remission at each Analysis Visit for the PAS. Boolean remission using 28-joint-count, 28-joint-count + feet and ankles, and 66/68 joint count will be assessed. Chi-squared test comparing etanercept monotherapy vs methotrexate monotherapy Chi-squared test comparing etanercept and methotrexate combination therapy vs methotrexate monotherapy	

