Disease-Worsening defined as an SDAI > 3.3 and ≤ 11 during two consecutive visits at least 2 weeks apart or SDAI > 3.3 and ≤ 11 on three or more separate visits or SDAI > 11 after randomization	Observed count (percentage) of subjects fulfilling Disease-Worsening criteria at each Analysis Visit for the PAS.	

Table 1. Primary and Secondary Endpoints Summary Table

Endpoint	Primary Analysis Method	Sensitivity/Exploratory Analysis
Secondary Endpoints (Continued)		
Time to Disease-Worsening as an SDAI > 3.3 and ≤ 11 during two consecutive visits at least 2 weeks apart or SDAI > 3.3 and ≤ 11 on three or more separate visits or SDAI > 11 after randomization	Kaplan-Meier curves, estimates, and 95% CIs assessing Time to Disease-Worsening by treatment group for the PAS. Subjects with more than one DW Date will be analyzed using the first DW Date. Subjects who do not experience disease-worsening will be censored at last SDAI assessment date. Log-rank test comparing etanercept monotherapy versus methotrexate monotherapy. Log-rank test comparing etanercept and methotrexate combination therapy versus methotrexate monotherapy.	
Time to recapture observed SDAI remission after starting rescue treatment	Kaplan-Meier curves assessing Time to recapture observed SDAI remission from Rescue Date for the Rescue Analysis Set. Subjects with more than one recapture of SDAI remission will be analyzed using their first recapture date. Subjects who do not recapture SDAI remission are censored at their last SDAI assessment date. Log-rank test comparing etanercept monotherapy versus methotrexate monotherapy. Log-rank test comparing etanercept and methotrexate combination therapy versus methotrexate monotherapy.	Similar analysis as the Primary Analysis Method but using the Disease-Worsening Analysis Set, looking at time to recapture SDAI remission from DW Date.
Observed SDAI remission at Week 48	Observed count (percentage) of subjects achieving SDAI remission as defined by Observed_SDAI_remission as detailed in Section 6.5 at Week 48 for the Rescue Analysis Set.	Similar analysis as the Primary Analysis Method but using the Disease-Worsening Analysis Set.

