“Rescue Baseline” is defined as the latest assessment on or before a subject’s rescue date.

Let $Visit_0$ = the Analysis Visit at which a subject initiates rescue, where Analysis Visit is for SDAI score and is defined in the Double-Blind Treatment Period Analysis Visits Table above.

Let $Visit_1$ represent the Analysis Visit on or after $Visit_0$.

Then $Rescue_visit$ will be defined as follows:

If subject has received rescue (Study Day Subject Received Rescue \leq Study Day):

- $Rescue_visit = 12$,
If $Visit_1 - Visit_0 = 0$ or 12
- $Rescue_visit = Visit_1 - Visit_0$,
Otherwise.

If a subject has not yet received rescue at a specific visit, $Rescue_visit$ missing.

If a subject has multiple observations for the same $Rescue_Visit$, the latest observation will be used in the analysis.

Efficacy Endpoint Scoring Algorithms

Abbreviations:

TEN28	28-joint Tender Joint Count
SW28	28-Joint Swollen Joint Count
PtGA	Patient Global Assessment
PhGA	Physician Global Assessment
ESR	Erythrocyte Sedimentation Rate

Simplified Disease Activity Index (SDAI)

The SDAI is a composite measure that sums the total number of tender and swollen 28-joint counts, the PtGA on a 0-10 scale, the PhGA on a 0-10 scale, and the CRP in mg/dL. PtGA and PhGA are collected in a 0-100 scale, so they will need to be divided by 10.

The SDAI is scored as follows:

$$\text{TEN28} + \text{SW28} + \text{PtGA}/10 + \text{PhGA}/10 + \text{CRP (mg/dL)}$$

Clinical Disease Activity Index (CDAI)

The CDAI is a further simplification of the SDAI that excludes the acute phase reactant. It sums the total number of tender and swollen 28-joint counts, the PtGA on a 0-10 scale and the PhGA on a 0-10 scale. PtGA and PhGA are collected in a 0-100 scale, so they will need to be divided by 10.

The CDAI is calculated using the following formula:

$$\text{TEN28} + \text{SW28} + \text{PtGA}/10 + \text{PhGA}/10$$

DAS28-CRP

A subject's DAS28-CRP score is calculated as follows:

$$\text{DAS28-CRP} = 0.56*\sqrt{\text{TEN28}} + 0.28*\sqrt{\text{SJC28}} + 0.36*\ln(\text{CRP}+1) + 0.014*\text{PtGA} + 0.96,$$

where CRP is measured in mg/L.

DAS28-ESR

A subject's DAS28-ESR score is calculated as follows:

$$\text{DAS28-ESR} = 0.56*\sqrt{\text{TEN28}} + 0.28*\sqrt{\text{SJC28}} + 0.70*\ln(\text{ESR}) + 0.014*\text{PtGA},$$

where ESR is measured in mm/hr.

Swollen Joint Count

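### A visit missing one SDAI component cannot count toward disease-worsening, even when the observed components already sum to more than 11 (or 3.3), and the subject then defaults to not worsened

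*SAP*

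**What the plan says.** - **Worsening.** SAP 6.1 (Disease-Worsening Date) states that "Disease-Worsening classification is based on observed SDAI values only", with an exception for the multiple-imputation analysis. Protocol 3.1.2 and SAP 6.5 give three criteria: SDAI above 3.3 and up to 11 at two consecutive visits at least two weeks apart, the same range at three or more visits, or "SDAI > 11 at anytime".
- **Missing components.** SAP 10.3.3: "Missing components of composite endpoints will not be imputed".
- **SDAI formula.** SAP Appendix A adds the 28-joint tender and swollen counts, the patient and physician global scores (each divided by 10) and CRP in mg/dL. It has no rule for a visit with one term missing.
- **Primary endpoint.** SAP 6.2 scores success if Week 48 SDAI is 3.3 or less and worsening was not fulfilled during the study. It scores missing if there is no Week 48 SDAI and no worsening, and failure otherwise. SAP 11.5.1.1 turns missing into non-response.
- **Other analyses.** SAP 11.5.2, Table 1, reports "Observed count (percentage) of subjects fulfilling Disease-Worsening criteria at each Analysis Visit for the PAS". For time to worsening, SAP 6.4 says: "The subjects without Disease-Worsening will be censored at their last SDAI assessment date". SAP 7.3 admits to the Disease-Worsening Analysis Set only randomized subjects who meet the definition.

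**The concern.** The Week 48 remission variable has a missing state, and non-responder imputation resolves it against the subject. Disease-worsening has no such state: a subject either fulfilled the definition or did not. A visit that cannot be scored therefore falls on the favourable side, even when the recorded components prove the opposite.

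The situation can arise in practice. Joint scores are entered on the site tablet (Protocol 7.3.8.1), while CRP comes from a central laboratory (Protocol 7.4), so CRP can be absent when the other four terms are present.

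The primary estimand in SAP 4.1.1 is remission at Week 48 without worsening on study. A subject with a certain but uncounted worsening who later returns to 3.3 or below would be scored as a success against that definition. The same subject would be event-free in time to worsening and left out of the Disease-Worsening Analysis Set.

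**Working it through.** **1. The partial sum is a lower bound.** Joint counts, global scores on a 0-100 scale and CRP cannot be negative, so SDAI is at least the sum of the observed terms. Illustration with CRP missing: tender 5, swollen 4, patient global 30, physician global 25 gives 5 + 4 + 3.0 + 2.5 = 14.5. SDAI is above 11 whatever the CRP. In a simulation that removed one term at random, 196,729 visits had a partial sum above 11, and none of them had a full SDAI of 11 or less.

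**2. The same holds for the lower threshold.** A partial sum above 3.3 proves SDAI above 3.3. If the unknown total were above 11, the visit would be worsening by itself. Counting it only as a visit above 3.3 therefore cannot create a worsening that the full data would have excluded.

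**3. How the visit is handled under the SAP.** One term is missing and is not imputed (10.3.3), so the formula gives no SDAI (Appendix A). Worsening uses observed SDAI (6.1), so the visit does not count. What follows depends on where the visit falls:

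| Incomplete, decisive visit | Result |
|---|---|
| Week 48, no earlier worsening | Primary status missing, then non-response: correct |
| Interim, worsening recorded later | Primary failure: correct; time to worsening delayed |
| Interim, no other worsening, Week 48 SDAI > 3.3 or missing | Primary failure: correct; worsening event lost |
| Interim, no other worsening, Week 48 SDAI ≤ 3.3 | **False success**; worsening event lost |

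**4. The plan's own figure, for scale.** SAP 3.2 gives 100 per arm for 72% versus 50%, two-sided 0.05, 90% power. The pooled chi-square formula gives 102 and the unpooled formula 99; power at 100 per arm is 89.7%. The planned size reproduces and does not depend on this point.

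**5. Size.** The documents give no rate of missing components, so both rates below are assumptions. Only Weeks 12, 24 and 36 matter for a false success:

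- interim visits per 100-subject arm: 3 × 100 = 300
- incomplete at 3%: 0.03 × 300 = 9
- decisive at 10-20%: 0.9 to 1.8 visits
- with 1% incomplete: 0.3 to 0.6; with 5%: 1.5 to 3.0

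These are visits. A change of primary status also needs no other recorded worsening and recovery to 3.3 or below, so fewer subjects are affected.

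**6. Ceiling on the treatment difference.** Suppose that every decisive visit became a false success, and only on methotrexate. The methotrexate rate would rise from 50% to 50.9-51.8%, and the difference would fall from 22.0 to 21.1-20.2 points. Power would fall from 89.7% to 87.1-84.2%. The real effect lies well inside this, because most such subjects would not meet all the conditions and some loss would occur on etanercept too.

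**The case against.** **The text does not say that a decisive partial sum is ignored.** In SAP 6.1 the word for observed is set against imputation, and the sentence exempts the multiple-imputation analysis. This is fair: the point is an inference from 6.1, 10.3.3 and the formula. But no other passage would let such a visit count. The exemption helps only in part, because SAP 11.5.1.2 imputes the whole score and not its components, so a drawn value can fall below the observed partial sum.

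**The route to the primary endpoint is narrow.** It needs an incomplete interim visit, a decisive sum, no other worsening and recovery. Extra Disease Assessment visits are available (Protocol 7.2.7). This stands, and it is why the effect is small.

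**A reader might infer that incomplete Week 48 visits become successes.** They do not; SAP 11.5.1.1 scores them as non-response.

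**A reader might extend the point to Boolean remission.** SAP 6.5 sets that status to missing "if any components of the Boolean remission definition are missing". A failed component is not itself set to missing: with all four observed, a failure scores 0. A failure with another component absent does drop out of the observed percentage. However, scoring only the known failures as 0 would push remission downward if components are missing at random. Scoring every incomplete record as non-remission would depart from the observed-cases rule for secondary endpoints in Protocol 10.5.1. The documents do not show that the present Boolean rule is biased, so no change to its main derivation is warranted.

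**Conclusion.** The point holds for SDAI-based worsening, as a minor gap in a derivation rule. Recorded data can prove that a subject worsened, yet the SAP leaves the subject as not worsened. Time to worsening, the worsening proportion and the Disease-Worsening Analysis Set are affected directly. The primary endpoint is affected only through an uncounted interim event followed by Week 48 remission.

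On assumed rates of 3% incomplete and 10-20% decisive, this is 0.9-1.8 interim visits per 100-subject arm, and fewer subjects. A reader might take those figures as subjects who change status; they are upper limits, because they count visits.

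A reader might also suspect that the gap favours etanercept. Under the plan's own assumption of less remission on methotrexate, more of the lost worsenings would be expected there, which slightly dilutes the difference and works against the superiority claim. The conclusion of the trial is unlikely to depend on it.

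**What to change.** Add to SAP 6.5, for the analysis derivation only and with the rescue trigger unchanged:

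- where one or more SDAI components are missing, a partial sum above 11 counts as SDAI above 11;
- a partial sum above 3.3 counts as a visit with SDAI above 3.3 for the two-visit and three-visit worsening criteria;
- SDAI at worsening and change from worsening stay missing for events established in this way.

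Align the sentence in SAP 6.1 with this rule. Leave the Boolean derivation as it is; at most, report a sensitivity analysis with all incomplete Boolean records scored as non-remission.

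The cost is a few lines of SAP text and a short programming change on data already collected, with no imputation model. The one downside is that the few events added have no SDAI value in the summaries that start from the worsening date. The rule should be fixed before unblinding.

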6.2 Primary Endpoint

Primary Endpoint - SDAI remission at week 48

The primary endpoint of SDAI remission is defined as achievement of SDAI \leq 3.3 at Week 48 without fulfilling the definition of disease-worsening during the study.

Primary endpoint of SDAI remission will be defined as follows:

- SDAI_remission_maintenance (\leq 3.3) at Week 48 = 1, if SDAI \leq 3.3 at Week 48 AND subject did not fulfill the definition of disease-worsening during the study;
- SDAI_remission_maintenance (\leq 3.3) at Week 48 = missing, if subject has no Week 48 SDAI value AND subject did not fulfill the definition of disease-worsening during the study;
- SDAI_remission_maintenance (\leq 3.3) at Week 48 = 0, otherwise.

Different statistical methods for addressing missing SDAI remission status are addressed in [Section 11.5](#).

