### Non-investigational Product

**Non-Amgen Non-investigational Product Dosage and Administration:** Folic acid dosing will be 5 to 7 mg per investigator judgment or administration according to local standard of care.

See [Section 6.3](#).

**Procedures:** Written informed consent must be obtained from all subjects before any screening procedures are performed. The following procedures will occur per the schedule of assessments: medical and medication history, physical examination, physical measures, vital signs, adverse event and concomitant medication assessment, tuberculosis testing, pregnancy testing, urinalysis, and blood draw for serum chemistry, hematology, hepatitis B and C testing, CRP and biomarkers, tender and swollen joint assessment and count and patient reported outcomes. For a full list of study procedures, including the timing of each procedure, please refer to [Section 7](#) and the Schedule of Assessments ([Table 1](#)).

**Statistical Considerations:** The primary endpoint for this study is SDAI remission (SDAI  $\leq 3.3$ ) at week 48. The proportion of subjects achieving this endpoint will be compared across treatment arms using the chi-square test. The etanercept monotherapy treatment arm will be compared to the methotrexate monotherapy arm. Both subjects who drop out and subjects receiving rescue therapy due to disease worsening during the double-blind period will be considered non-responders. Furthermore, the randomized subjects who did not receive any dose of any of the investigational products will be considered non-responders in the primary analysis. As a sensitivity analysis, subjects who receive rescue therapy or drop out will have their post-rescue SDAI responses set to missing and a multiple imputation technique to impute these values will be employed.

[figure not shown]
Summary statistics will be provided for endpoints listed in this protocol. For categorical endpoints, the summary statistics contain the frequency and percentage. For continuous endpoints, the summary statistics contain number of observations, mean, standard deviation, standard error, median, minimum, maximum, and 95% confidence interval. For a full description of statistical analysis methods, please refer to [Section 10](#).

**Sponsor:** Amgen Inc.

Data Element Standards  
Version(s)/Date(s):

Version 4.0 31 October 2013

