### **10.5.2 Primary Efficacy Endpoint**

The primary analysis for the primary endpoint for this study, SDAI remission at week 48, will be performed using the primary analysis set. The primary endpoint will be measured by the proportion of subjects who maintain SDAI remission ( $SDAI \leq 3.3$ ) at week 48.

SDAI remission at week 48 for the etanercept monotherapy treatment arm will be compared to the methotrexate monotherapy arm using the chi-square test.

Both subjects who drop out and subjects receiving rescue therapy due to disease worsening during the double-blind period will be considered non-responders.

Furthermore, the randomized subjects who did not receive any dose of any of the investigational products will be considered non-responders in the primary analysis.

As a sensitivity analysis, subjects who receive rescue therapy or that drop out will have their post-rescue SDAI responses set to missing and a multiple imputation technique to impute these values will be employed. The multiple imputation method is less

conservative than the non-responder imputation method and will be prospectively described in more detail in the SAP.

A subject's SDAI score is calculated as follows:

SDAI = 28-joint tender joint count + 28-joint swollen joint count + Patient Global Assessment of Disease Activity + Physician Global Assessment of Disease Activity + C-reactive protein (mg/dL).

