6.5 Study Endpoints

Patient Global Assessment of Joint Pain (PtGAJP)

An assessment of the severity of the subject's joint pain (0=no pain at all, 100=worst pain imaginable) completed by the patient using a visual analog scale (VAS) in mm.

Patient Global Assessment of Disease Activity (PtGA)

A global assessment of the subject's arthritis (0=no arthritis activity at all, 100=worst arthritis activity imaginable) completed by the patient using a visual analog scale (VAS).

Physician Global Assessment of Disease Activity (PhGA)

A global assessment of the subject's arthritis (0=no activity at all, 100=worst activity imaginable) completed by the physician using a visual analog scale (VAS).

Swollen Joint Count

A score that assesses the presence or absence of swelling in 66 joints. There are also a 28-joint Swollen Joint Count and a 28-joint Plus Feet and Ankles Swollen Joint Count. Details of the scoring algorithm are described in [Appendix A](#).

Tender Joint Count

A score that assesses the presence or absence of tenderness in 68 joints. There are also a 28-joint Tender Joint Count and a 28-joint Plus Feet and Ankles Tender Joint Count. Details of the scoring algorithm are described in [Appendix A](#).

Simplified Disease Activity Index (SDAI)

A composite score that is based on the number of tender and swollen joints using a 28-joint count, PhGA (0-10 visual analog scale), PtGA (0-10 visual analog scale), and CRP in mg/dL. A higher score represents worse disease.

Details of the scoring algorithm are described in [Appendix A](#).

SDAI Remission at Analysis Visit k

For Analysis Visits other than Week 48, SDAI Remission at a given Visit will be derived using the same approach as in [Section 6.2](#), replacing Week 48 with the Analysis Visit Week k , and replacing “subject did not fulfill the definition of disease-worsening during the study” with “subject did not *previously* fulfill the definition of disease-worsening”.

Specifically,

- SDAI_remission_maintenance (≤ 3.3) at Week $k = 1$,
if SDAI ≤ 3.3 at Week k AND subject did not previously fulfill the definition of disease-worsening;
- SDAI_remission_maintenance (≤ 3.3) at Week $k = \text{missing}$,
if subject has no Week k SDAI value AND subject did not previously fulfill the definition of disease-worsening;
- SDAI_remission_maintenance (≤ 3.3) at Week $k = 0$,
otherwise.

Observed SDAI Remission at Analysis Visit k

- Observed_SDAI_Remission at Analysis Visit $k = 1$,

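### SAP 6.2 scores the primary endpoint on observed disease worsening alone and omits the protocol's rescue rule, so a rescued subject can count as a responder

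*SAP*

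**What the plan says.** Protocol 10.5.2 sets the rule for the primary endpoint: "Both subjects who drop out and subjects receiving rescue therapy due to disease worsening during the double-blind period will be considered non-responders". The Synopsis, under Statistical Considerations, repeats it. Protocol 3.1.2 defines worsening through SDAI, and one of its three criteria is "SDAI > 11 at anytime". Under 3.1.1 worsening leads to rescue, dispensed through IXRS.

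SAP 6.2 derives SDAI_remission_maintenance in three branches:

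- 1 when week-48 SDAI is at most 3.3 "AND subject did not fulfill the definition of disease-worsening during the study";
- missing when there is no week-48 SDAI and no worsening;
- 0 otherwise.

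Rescue appears in none of them. On worsening, SAP 6.1 says: "With the exception of analysis using multiple imputation method, Disease-Worsening classification is based on observed SDAI values only". SAP 10.3.3 adds: "Missing components of composite endpoints will not be imputed". SAP 6.1 defines rescue separately, from the rescue dosing forms: a subject's "rescue date is the Visit Date in which he or she first receives rescue therapy".

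SAP 11.5.1.1 applies non-responder imputation when the endpoint cannot be derived because SDAI is missing. SAP 11.5.1.2 adds a multiple-imputation analysis in which SDAI after rescue is set to missing. SAP Section 12 cites Protocol 10.5.2 but alters only its sentence on subjects who never received a dose.

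**The concern.** Rescue is a dosing event. Observed worsening is a derived classification that needs a complete SDAI. The protocol scores on the first and the SAP on the second. Where they part, a subject who was returned to both drugs can be counted as having maintained remission on one of them. This affects the primary endpoint variable, which also serves the combination versus methotrexate comparison, and the list of changes from the protocol does not mention it. In the combination arm the assigned treatment simply continues after rescue, so there the only effect is that the protocol's scoring rule is not applied.

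**Working it through.** **1. Where the rules differ.** Cross rescue (yes/no), observed worsening (yes/no) and week-48 SDAI (at most 3.3, above 3.3, missing): 12 combinations. If week-48 SDAI is above 3.3 or missing, both rules end at 0, using non-responder imputation where needed. Four combinations remain, all with week-48 SDAI of 3.3 or less:

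| Rescued | Observed worsening | Protocol 10.5.2 | SAP 6.2 |
|---|---|---|---|
| no | no | 1 | 1 |
| yes | yes | 0 | 0 |
| yes, for worsening | no | 0 | **1** |
| no | yes | not expressly scored (1 if read literally) | **0** |

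The third row is the point at issue. In the fourth the SAP is the stricter document.

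**2. Can the third row occur under the documents' own rules?** Suppose that at the visit leading to rescue CRP is missing, the 28-joint tender count is 4, the swollen count is 3, the patient global is 25 mm and the physician global is 20 mm (illustrative values). By the SDAI formula in SAP Appendix A, the four available terms give 4 + 3 + 25/10 + 20/10 = 11.5. CRP cannot be negative, so SDAI exceeds 11 and the protocol's criterion is met. The SAP has no SDAI value at that visit, hence no worsening. If no other observed visit meets the definition and week-48 SDAI is at most 3.3, SAP 6.2 returns 1. Non-responder imputation does not act, because the endpoint is derivable. The subject also falls outside the Disease-Worsening and Rescue Analysis Sets (SAP 7.3 and 7.4), since both require the worsening definition.

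**3. The plan's own sample size.** Inputs from Protocol 10.2: 50% v 72%, two-sided 0.05, 90% power, 100 per arm. Mean rate 0.61, difference 0.22.

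- Pooled variance: [1.96·√(2·0.61·0.39) + 1.2816·√(0.25 + 0.2016)]² / 0.22² = (1.352 + 0.861)² / 0.0484 = 101.2, so 102 per arm.
- Unpooled variance: (1.96 + 1.2816)²·0.4516 / 0.0484 gives 99 per arm.
- Power at 100 per arm: Φ[(0.22·√100 − 1.352) / 0.672] = Φ(1.262) = 89.7%.

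The stated 100 per arm is reproduced.

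**4. Effect of misscored subjects.** Chi-square without continuity correction: z = difference / √[p̄(1 − p̄)·2/100].

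- 72 v 50: 0.22 / √(0.61·0.39·0.02) = 3.19, p = 0.0014.
- 72 v 58 (eight misscored methotrexate subjects): 0.14 / √(0.65·0.35·0.02) = 2.08, p = 0.038.
- 72 v 59 (nine): 0.13 / √(0.655·0.345·0.02) = 1.93, p = 0.053.

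With continuity correction, eight are enough (72 v 58, p = 0.054).

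Power from the formula in step 3, treating each misscored subject as one percentage point in that arm:

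- one methotrexate subject: 86.8%;
- two methotrexate subjects: 83.5%;
- one etanercept subject: 92.3%.

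A borderline table can change with one subject: 64 v 50 gives p = 0.046, and 64 v 51 gives p = 0.063.

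**The case against.** The strongest reply is that the two rules coincide in intended conduct. Rescue is triggered by the same SDAI-based definition, the sponsor calculates SDAI (Protocol 7.3.8.3), IXRS controls dispensing, and CRP is scheduled at every double-blind and Disease Assessment visit. The example needs a missing component at the trigger visit, rescue dispensed all the same, no observed worsening elsewhere, and week-48 remission. Nothing in the documents shows that this happens. This stands as a limit on frequency. It does not show that the rules are the same: the SAP takes rescue from dosing forms, requires worsening and rescue doses as separate conditions in 7.4, and accepts in Section 12 that worsening may occur without rescue. CRP goes to a central laboratory (Protocol 7.4), and the documents do not say that a calculated SDAI must exist before rescue is dispensed.

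Second, the multiple-imputation analysis would delete and impute the post-rescue week-48 value in the example. That is correct and may reveal dependence on such subjects. It is a sensitivity analysis and leaves the primary score as it is.

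Third, SAP 4.1.1 openly states the estimand in terms of worsening. It does, but it does not say that the protocol's rescue rule has been dropped. The remark in Section 12 about using observed week-48 values concerns, in context, subjects who were never dosed.

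A reader might also infer that the week-k rule in SAP 6.5, which requires that SDAI be at most 3.3 "AND subject did not previously fulfill the definition of disease-worsening", replaces a protocol rescue rule in the same way. The documents do not support this. The protocol's rule belongs to the primary endpoint, and Protocol 10.5.1 plans observed cases for secondary endpoints. At other visits there was no rescue rule to replace.

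**Conclusion.** The departure is real but minor. SAP 6.2 leaves out a condition that Protocol 10.5.2 attaches to the primary endpoint, and Section 12 does not record it. The number affected is not in the documents; the working shows one or two subjects as an assumed case, and there may be none. A misscored methotrexate subject narrows the difference and a misscored etanercept subject widens it, so no systematic bias is shown. At the planned rates the conclusion survives up to eight misscored methotrexate subjects (seven with continuity correction). Only a borderline result could turn on this.

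A reader might take worsening without rescue (SAP 0) as a second contradiction. It is not one: Protocol 3.1.1 expects a worsening subject to start rescue, and 10.5.2 does not expressly score a subject who does not. It needs recording, not reversing.

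**What to change.** 1. In SAP 6.2, set SDAI_remission_maintenance to 0 if the disease-worsening definition is met **or** the subject has a Rescue Date (SAP 6.1) before the week-48 assessment.
2. In Section 12, record that any rescue counts as non-response, which is slightly broader than the protocol's restriction to rescue for worsening, and that worsening without rescue is also scored 0.
3. Before unblinding, count, pooled over arms, the subjects with a Rescue Date and no Disease-Worsening Date. A count of zero means that adding the rescue condition changes no subject's score.

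A rescue term in the week-k rule of 6.5 is optional, for consistency with 6.2 only.

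The cost is one condition in one derivation, two sentences in Section 12 and one blinded count. No new data are needed, and the sample size, worsening endpoints and analysis sets stay as they are.
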